### **9.3. Statistical Methods and Analytical Plan**

Additional details of the proposed statistical analysis will be documented in the statistical analysis plan (SAP), which will be written following finalization of the protocol and prior to study unblinding / analysis (as appropriate).

Document Name	Protocol 206827 CCI doc		
Type	Version	Document Identifier	Effective Date
elido controlled	4.0; Most-Recent; Effective; CURRENT	090032d580d98eb9	15-Sep-2017 09:27:15
Reason For Issue	Auto Issue		

### 9.3.1. Demographic and Baseline Characteristics

Age will be summarized descriptively for each product group using means, medians and standard deviations. Race, gender, Fitzpatrick phototype and Glogau photoaging type will be summarized by product group using frequency counts and percentages.

### 9.3.2. Primary Analysis(es)

Descriptive statistics (N, %, 95% confidence intervals) will be used to summarize the proportion of subjects in each product group with a favorable Evaluator global assessment of tolerance. The proportions may also be compared between product groups using Chi-square test, and difference in proportion and 95% confidence interval.

### 9.3.3. Secondary Analysis(es)

Changes from baseline in the Evaluator, Subject self-assessment and instrumental endpoints will be tabulated by product group and summarized descriptively using means, standard deviations and 95% confidence intervals and assessed for significance (different from zero) using t-tests or Wilcoxon signed rank tests dependent upon the distribution of the data.

Differences between product groups in the mean changes from baseline in Evaluator, Subject self-assessment and instrumental endpoints will also be explored using t-tests or Wilcoxon rank sum tests and summarised using 95% confidence intervals.

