## 2. OBJECTIVE(S) AND ENDPOINT(S)

Objective(s)	Endpoint(s)
Primary	
Assessment of the local tolerance of the test product in subjects who have undergone a 70% Glycolic Acid facial peel	Evaluator (Dermatologist) global assessment of tolerance
Secondary	
Assessment of skin recovery (change from baseline) over a period of 14 days in subjects who have undergone a 70% Glycolic Acid facial peel	Combined (sum of) Evaluator (Dermatologist) scores for signs/symptoms of erythema, edema, desquamation and dryness  Individual Evaluator (Dermatologist) scores for erythema, edema, desquamation and dryness  Combined (sum of) subject self-assessment scores for redness, pain, stinging/burning, itching, tightness and dryness  Individual subject self-assessment scores for redness, pain, stinging/burning, itching, tightness and dryness  Instrumental measurement of barrier function (Tewameter) and moisturisation (Corneometer)  Subject global self-assessment
Assessment of skin recovery (change from baseline) between treatment groups.	All assessments and measurements listed above

Document Name	Protocol 206827 CCI doc	Document Identifier	Effective Date
Type	Version		
eldo controlled	4.0; Most-Recent; Effective; CURRENT	090032d580d98eb9	15-Sep-2017 09:27:15

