Document Name	Protocol 206827 CCI doc		
Type	Version	Document Identifier	Effective Date
eldo controlled	4.0; Most-Recent; Effective; CURRENT	090032d580d98eb9	15-Sep-2017 09:27:15
Reason For Issue	Auto Issue		

the cutaneous damage for both groups, making it more difficult to measure a cosmetic benefit over time. Barrier function was observed to gradually worsen over the duration of the study, with weak indications of improvement between days 4 and 7. There was no statistically significant barrier function benefit between groups at any time point.

Based on this literature review, subject visits have been included at 24-72 hours post-procedure, where differences between control and test groups are expected to be largest. While it is expected the skin's barrier function will return to normal 24 to 48 hours following the procedure, the total duration of the test phase is 14 days to enable sufficient time to monitor desquamation and erythema compared to the post-procedure, pre-treatment baseline.

Document Name	Protocol 206827 CCI doc		
Type	Version	Document Identifier	Effective Date
elido controlled	4.0; Most-Recent; Effective; CURRENT	090032d580d98eb9	15-Sep-2017 09:27:15
Reason For Issue	Auto Issue		

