### 6.3.10. Instrumental Measurements Pre-Procedure

Instrumental measurements of Transepidermal Water Loss and skin hydration will be conducted by the Investigator or designee and recorded on the eCRF. Subjects will acclimatize to the controlled room temperature ( $21\pm1$  °C) and humidity ( $50\pm10\%$ ) for at least 30 minutes prior to instrumental assessment.

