### 6.3.14. Dermatological Procedure (Facial Peel)

The 70% Glycolic Acid facial peel procedure will be conducted by a medically qualified professional with hands-on experience administering peels of this nature. The site will source 70% Glycolic Acid treatment (SM Empreendimentos Farmacêuticos (Fagron)) and Sodium Bicarbonate neutralizing solution (Labsynth Produtos para Laboratórios (Synth)) from MagisPharma and will retain a copy of the purchase order and certificate of analysis, which will be stored in the Trial Master File (TMF).

Prior to the Glycolic Acid treatment, the subject's skin will be degreased by wiping with a gauze soaked in an alcohol solution (70% (w/w) in water). A fresh gauze will

Document Name	Protocol 206827 CCI doc		
Type	Version	Document Identifier	Effective Date
elido controlled	4.0; Most-Recent; Effective; CURRENT	090032d580d98eb9	15-Sep-2017 09:27:15
Reason For Issue	Auto Issue		

then be soaked in the 70% Glycolic Acid solution, which will be applied evenly over the entire face (excluding eyelids) starting in the center and moving to the periphery of the face. The Glycolic Acid solution will remain in contact with the skin for a minimum of 1 minute and a maximum of 3 minutes. The dermatologist will determine the exact treatment time on a subject by subject basis by monitoring their individual response to treatment. The dermatologist may determine that it is in the interests of the subject to terminate the treatment phase sooner than 1 minute after initial application. This will be considered a protocol deviation and recorded on the Deviations Log. Similarly, a treatment phase of longer than 3 minutes will be reported as a deviation. Subjects who do not receive at least 1 minute or who receive more than 3 minutes of Glycolic Acid treatment will still be considered eligible to continue the study unless the dermatologist believes them otherwise unsuitable to continue (e.g. for safety reasons).

Once the Glycolic Acid treatment period is complete, a fresh gauze will be soaked with the sodium bicarbonate solution, which will be applied evenly over the entire face (excluding eyelids) starting in the center and moving to the periphery of the face. This process will be repeated until the dermatologist considers the Glycolic Acid solution to be successfully neutralized. The dermatologist will then rinse the subject's face thoroughly with water.

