### **6.3.16. Instrumental Measurements Post-Procedure, Pre-Treatment (BASELINE)**

Assessments to be taken and recorded as per 6.3.10, 60±15 minutes after completion of the facial peel procedure.

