## 9. STATISTICAL CONSIDERATIONS AND DATA ANALYSES

### 9.1 Sample Size Determination

Approximately 130 **178** healthy females within the ages of 30 and 60 years with Fitzpatrick Skin Classification II-IV and moderate to advanced photo-damaged skin will be screened to randomize 80 **100** subjects to ensure approximately 60 **80** subjects (**30 40** subjects per group) successfully complete the study. The sample size is based on clinical considerations and literature precedent [Narurkar, Schalka, Sulimovic, Kim].

~~With 30 subjects per treatment group, a change from baseline in TEWL at least half the magnitude of the standard deviation (e.g. assume std=4 (ref. **CCI** [REDACTED]), and 2.1 point mean change from baseline) can be detected at two-sided alpha=0.05 with 80% power.~~

**THE FIRST 10 SUBJECTS WERE MIS-ALLOCATED TREATMENT. TO PROTECT THE STATISTICAL POWER OF THE STUDY FOR THE SECONDARY TEWL ENDPOINT, 20 ADDITIONAL SUBJECTS WILL BE RECRUITED INTO THE STUDY. WITH 100 SUBJECTS RANDOMISED, 80 SUBJECTS (40 SUBJECTS PER GROUP) ARE EXPECTED TO COMPLETE THE STUDY.**

**WITH 40 SUBJECTS PER TREATMENT GROUP WITH 5 SUBJECTS PER GROUP RECEIVING THE INCORRECT TREATMENT DUE TO MIS-ALLOCATION, A WITHIN CHANGE FROM BASELINE IN TEWL OF 1.83 CAN BE DETECTED AT TWO-SIDED ALPHA=0.05 WITH AN SD=4.053 AND 80% POWER.**

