#### **9.2.4. Criteria for Assessing Efficacy**

Efficacy measurements in this study will be based on changes from baseline in TEWL and Corneometer values at each visit. The baseline for these measurements will be defined as the measurements made 60±15 minutes after the facial peel procedure, before any test product application. Differences between product groups will also be explored.

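### Section 9.3.3 names an unadjusted test on change for the between-group TEWL and Corneometer comparison, although the recorded post-peel baseline could be used as a covariate at no cost (minor, free improvement)

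*Protocol*

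**What the plan says.** Section 2 of the protocol lists two secondary objectives. One is skin recovery over 14 days. The other is "Assessment of skin recovery (change from baseline) between treatment groups", which covers all the same assessments, including TEWL and Corneometer.

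Section 9.2.4 makes change from baseline in these two instruments the efficacy measure and adds: "Differences between product groups will also be explored". Section 9.3.3 names the method. Between-group differences in mean change "will also be explored using t-tests or Wilcoxon rank sum tests and summarised using 95% confidence intervals". No covariate-adjusted model appears anywhere in the protocol.

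The instrumental baseline is taken at Visit 3, after the peel and before product is dispensed: "Assessments to be taken and recorded as per 6.3.10, 60±15 minutes after completion of the facial peel procedure" (section 6.3.16). A pre-peel value is also recorded (section 6.3.10). Section 9.1 gives one power statement, for the within-arm contrast: with 40 per group, "A WITHIN CHANGE FROM BASELINE IN TEWL OF 1.83 CAN BE DETECTED AT TWO-SIDED ALPHA=0.05 WITH AN SD=4.053 AND 80% POWER".

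**The concern.** A t-test on change scores subtracts the whole baseline from each follow-up value, which forces a slope of 1. If the true slope differs from 1, the subtraction leaves avoidable noise in the comparison. ANCOVA estimates the slope from the data.

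The post-peel baseline may well differ between women, because contact time with the acid varies: "The dermatologist will determine the exact treatment time on a subject by subject basis by monitoring their individual response to treatment" (section 6.3.14). The protocol does not quantify that spread, so it is a reason to look and does not measure the gain.

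What is at stake is the width of the confidence interval for the product difference in two secondary endpoints, with about 40 women per arm. Bias is not at stake. The baseline follows randomisation but precedes any product, and the dermatologist giving the peel must be blind to allocation (Schedule of Events, note 9). It is therefore a legitimate covariate.

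**Working it through.** **Inputs from the protocol (section 9.1).** 40 completers per group, SD 4.053 (4 in the synopsis), two-sided alpha 0.05, power 80%, and 5 subjects per group who received the wrong treatment. I take the SD to be that of the change score.

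**Assumed inputs.** The baseline/follow-up correlation ρ, and k = baseline SD / follow-up SD. The protocol gives neither, so a range is shown.

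**1. The plan's own figure.** One-sample t-test, n = 40, change 1.83, SD 4.053. The noncentrality is 1.83/4.053 × √40 = 2.856 on 39 df, which gives power of 79.5%. The figure in 9.1 reproduces.

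**2. The named between-group test.** Two-sample t on change, 40 per arm, 78 df, SD 4.
- Standard error = 4 × √(2/40) = 0.894.
- 95% CI half-width = 1.991 × 0.894 = 1.78.
- Difference detectable with 80% power (noncentral t) = 2.54, or 2.57 at SD 4.053.

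**3. ANCOVA on the post-peel baseline.** Variance relative to the change score = (1 − ρ²) / (1 + k² − 2ρk), with 77 df. When k = 1 this reduces to (1 + ρ)/2. Detectable differences use 40 per arm and SD of change 4.

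| k | ρ | variance ratio | detectable difference | CI half-width |
|---|---|---|---|---|
| 1 | 0.3 | 0.65 | 2.05 | 1.44 |
| 1 | 0.5 | 0.75 | 2.20 | 1.54 |
| 1 | 0.7 | 0.85 | 2.34 | 1.64 |
| 1.25 | 0.3 to 0.7 | 0.50 to 0.63 | 1.80 to 2.01 | 1.26 to 1.41 |
| 0.75 | 0.3 to 0.7 | 0.82 to 0.995 | 2.30 to 2.53 | 1.61 to 1.78 |
| 0.7 | 0.7 | 1.00 | 2.54 | 1.78 |

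In the last row k = ρ, so the true slope is 1 and the change score is already the best choice. ANCOVA then only loses one degree of freedom (2.538 against 2.537). At k = 1 and ρ = 0.9 the detectable difference is 2.47, a gain of about 2.5%.

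**4. Simulation.** With k = 1, SD of change 4.053, a true difference of 2.57 and 4,000 runs per ρ, the t-test on change had power of about 81% throughout. ANCOVA had 93.8%, 90.1% and 85.3% at ρ = 0.3, 0.5 and 0.7.

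**5. Mis-allocation.** Steps 2 to 4 assume a clean 40 v 40 contrast. Suppose the 5 mis-allocated women per group are among the 40 and are analysed as randomised. The expected difference then shrinks to (35 − 5)/40 = 0.75 of the true effect. Holding the SD fixed, the detectable true effect of the unadjusted test becomes 2.537/0.75 = 3.38 at SD 4 and 2.571/0.75 = 3.43 at SD 4.053. If these women are left out (35 per arm), it is 2.72 and 2.75. The dilution applies to both methods, so the variance ratios in step 3 stand.

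**The case against.** The strongest reply is that nothing here is an error. A two-sample test on change is valid under randomisation, the comparison is only to be explored, and section 9.3 leaves further detail to an SAP that could add an adjusted model. That stands as far as validity goes. The protocol does name the test, however, and a better one is available from data it already collects. A free improvement is all that is claimed.

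The second reply is that the size of the gain is unknown. This stands in full. The range runs from nil to substantial, and the protocol does not say where this trial lies.

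Three stronger readings are tempting, and the documents do not support them.
- A reader might infer that 9.1 is wrong because it powers a within-arm change. It is labelled as within-arm, it reproduces, and it fits the first secondary objective.
- A reader might infer that the plan lets natural recovery pass as product benefit, since section 3.4 expects that "barrier function will return to normal 24 to 48 hours following the procedure" without reference to product. But section 2 lists recovery over time and the between-group difference as separate objectives, and no section bases a claim of benefit on the within-arm test.
- A reader might want a between-arm detectable difference of 2.5 to 2.6 added to 9.1. Beside the mis-allocation text that would be optimistic, because an as-randomised analysis that includes those women gives about 3.4.

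**Conclusion.** The point holds as a minor, free improvement. For TEWL and Corneometer, section 9.3.3 names a valid test that forgoes whatever precision the post-peel baseline offers. With equal variances and a correlation of 0.3 to 0.7, adjustment lowers the variance by 35% to 15%. If the baseline is less variable than the follow-up, the gain can disappear, and the cost is then one degree of freedom. These figures rest on an assumed correlation and variance ratio. The absolute detectable differences also rest on reading SD 4 as the SD of change and on ignoring the mis-allocated women. The primary tolerance endpoint and its success criterion are unaffected.

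**What to change.** In section 9.3.3, state that the between-group difference in TEWL and Corneometer at each visit is analysed by ANCOVA with arm and the post-peel baseline as terms, reporting the adjusted difference and its 95% confidence interval. Keep rank-based tests for the ordinal scores and for clearly non-normal data. Leave 9.1 as it is.

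The cost is one model and a sentence or two of text, with no extra subjects, visits or measurements.

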### 9.3.4. Safety Analysis(es)

Adverse events will be tabulated by product group and listed for inspection.

## 10. STUDY GOVERNANCE CONSIDERATIONS

### 10.1. Posting of Information on Publicly Available Clinical Trials Registers

Study information from this protocol will be posted on publicly available clinical trial registers before enrollment of subjects begins.

### 10.2. Regulatory and Ethical Considerations, Including the Informed Consent

The study will be conducted in accordance with all applicable regulatory requirements, and with GSK policy.

Document Name	Protocol 206827 CCI doc		
Type	Version	Document Identifier	Effective Date
elido controlled	4.0; Most-Recent; Effective; CURRENT	090032d580d98eb9	15-Sep-2017 09:27:15
Reason For Issue	Auto Issue		

The study will also be conducted in accordance with ICH Good Clinical Practice (GCP), all applicable subject privacy requirements, and the guiding principles of the current version of the Declaration of Helsinki. This includes, but is not limited to, the following:

- Before initiating a trial, the investigator/institution should have written and dated approval/favorable opinion from the IEC for the trial protocol (including amendments), written informed consent form, consent form updates, subject recruitment procedures (e.g., advertisements), investigator brochure/ safety statement (including any updates) and any other written information to be provided to subjects. A letter or certificate of approval will be sent by the investigator to the sponsor prior to initiation of the study, and also when subsequent amendments to the protocol are made.
- Signed informed consent to be obtained for each subject before participation in the study (and for amendments as applicable)
- Investigator reporting requirements (e.g. reporting of AEs/SAEs/protocol deviations to IEC)
- GSK will provide full details of the above procedures, either verbally, in writing, or both.

### 10.3. Quality Control (Study Monitoring)

In accordance with applicable regulations including GCP, and GSK procedures, GSK or designee (i.e. third party vendor) monitors will contact the site prior to the start of the study to review with the site staff the protocol, study requirements, and their responsibilities to satisfy regulatory, ethical, and GSK requirements.

When reviewing data collection procedures, the discussion will include identification, agreement and documentation of data items for which the eCRF will serve as the source document.

GSK or designee will monitor the study and site activity to verify that the:

- Data are authentic, accurate, and complete.
- Safety and rights of subjects are being protected.
- Study is conducted in accordance with the currently approved protocol and any other study agreements, GCP, and all applicable regulatory requirements.

The extent and nature of monitoring will be described in a written monitoring plan on file at GSKCH. The investigator (or designee) agrees to allow the monitor direct access to all relevant documents and agrees to co-operate with the monitor to ensure that any problems detected in the course of these monitoring visits are resolved.

Document Name	Protocol 206827 CCI doc		
Type	Version	Document Identifier	Effective Date
elido controlled	4.0; Most-Recent; Effective; CURRENT	090032d580d98eb9	15-Sep-2017 09:27:15
Reason For Issue	Auto Issue		

## 10.4. Quality Assurance

To ensure compliance with GCP and all applicable regulatory requirements, GSK may conduct a quality assurance assessment and/or audit of the site records, and the regulatory agencies may conduct a regulatory inspection at any time during or after completion of the study.

In the event of an assessment, audit or inspection, the investigator (and institution) must agree to grant the advisor(s), auditor(s) and inspector(s) direct access to all relevant documents and to allocate their time and the time of their staff to discuss the conduct of the study, any findings/relevant issues and to implement any corrective and/or preventative actions to address any findings/issues identified.

The sponsor will be available to help investigators prepare for an inspection.

## 10.5. Conditions for Terminating the Study

Upon completion or premature discontinuation of the study, the GSKCH monitor will conduct site closure activities with the investigator or site staff, as appropriate, in accordance with applicable regulations including GCP, and GSKCH Standard Operating Procedures.

Both GSKCH and the Investigator reserve the right to temporarily suspend or prematurely discontinue this study at any time for reasons including, but not limited to, safety or ethical issues or severe non-compliance. For multicenter studies (if applicable), this can occur at one or more or at all sites.

If the trial is prematurely terminated or suspended for any reason, the investigator site should promptly inform the trial subjects and should assure appropriate therapy/ follow-up for the subjects. Where required by the applicable regulatory requirements, GSKCH should inform the regulatory authority(ies).

In addition:

1. If the investigator terminates or suspends a trial without prior agreement of GSKCH, the investigator site should promptly inform the sponsor and the IEC, and should provide the sponsor and the IEC a detailed written explanation of the termination or suspension.
2. If the GSKCH terminates or suspends a trial, the investigator should promptly inform the IEC and provide the IEC a detailed written explanation of the termination or suspension.
3. If the IEC terminates or suspends its approval/favorable opinion of a trial, the investigator should promptly notify the GSKCH and provide GSKCH with a detailed written explanation of the termination or suspension.

Document Name	Protocol 206827 CCI doc		
Type	Version	Document Identifier	Effective Date
elido controlled	4.0; Most-Recent; Effective; CURRENT	090032d580d98eb9	15-Sep-2017 09:27:15
Reason For Issue	Auto Issue		

## 10.6. Records Retention

Following closure of the study, the investigator must maintain all site study records (except for those required by local regulations to be maintained elsewhere), in a safe and secure location.

The records (study/ site master file) must be maintained to allow easy and timely retrieval, when needed (e.g., for a GSK audit or regulatory inspection) and must be available for review in conjunction with assessment of the facility, supporting systems, and relevant site staff.

Where permitted by local laws/regulations or institutional policy, some or all of these records can be maintained in a format other than hard copy (e.g., microfiche, scanned, electronic); however, caution needs to be exercised before such action is taken.

The investigator must ensure that all reproductions are legible and are a true and accurate copy of the original and meet accessibility and retrieval standards, including re-generating a hard copy, if required. Furthermore, the investigator must ensure there is an acceptable back-up of these reproductions and that an acceptable quality control process exists for making these reproductions.

The investigator must assure that the subject's anonymity will be maintained. On eCRFs or other documents submitted to GSKCH, subjects should not be identified by their names or initials, but by an identification code. The investigator should keep a separate log of subjects' codes, names and addresses. Documents not for submission to GSKCH, e.g. subjects' written consent forms, should be maintained by the investigator in strict confidence.

GSK will inform the investigator of the time period for retaining these records to comply with all applicable regulatory requirements (GSKCH recommends that documents be kept for 10 years). The investigator is also required to keep subject identification codes on file for at least 15 years after completion or discontinuation of the study. The minimum retention time will meet the strictest standard applicable to that site for the study, as dictated by any institutional requirements or local laws or regulations, GSK standards/procedures, and/or institutional requirements.

No study document should be destroyed without a prior written agreement between GSKCH and the investigator. The investigator must notify GSK of any changes in the archival arrangements, including, but not limited to, archival at an off-site facility or transfer of ownership of the records in the event the investigator is no longer associated with the site.

Document Name	Protocol 206827 CCI doc		
Type	Version	Document Identifier	Effective Date
elido controlled	4.0; Most-Recent; Effective; CURRENT	090032d580d98eb9	15-Sep-2017 09:27:15
Reason For Issue	Auto Issue		

